11.2 Compliance

School staff who deliver ZF SEND will be trained in its delivery through successful completion of a one day training course. Qualitative interviews with school staff will examine the perceived quality and value of the training, and we will also conduct interviews with two trainers to explore the extent to which the training was delivered as intended. Fidelity of implementation of ZF SEND sessions in the classroom will be evaluated via self-rating by teachers for all sessions using intervention checklists. This will provide data on: the proportion of sessions delivered; whether each activity within a session is completed/partially completed; any factors which disrupted/aided delivery of

activities. In each school we will video record a sample of sessions, which include both children and teachers, this information, the information collected will be coded using the teacher checklist, and an additional tool that covers quality of delivery, any adaptations made to the materials during delivery, class dynamics and contextual issues, with space for free text qualitative observations. Where video recording is not possible (e.g. schools refuse permission) we will use either audio recording or direct observation by a researcher. Rates of agreement to allow video recording, teacher completion of fidelity checklists, and feedback from teachers and research staff will enable us to refine procedures for assessing fidelity within a future definitive trial. Interviews with school staff will be used to explore: adherence to the ZF SEND manual and key influences on implementation; any additions/adaptations made to the manualised content and the reasons for these; engagement in the intervention by pupils and their parents/carers; the perceived value of ZF SEND, and its fit with existing school policies/priorities; staff views on intervention aims and the mechanisms through which it operates. Data on factors affecting implementation across schools, and variations in fidelity/adaptions will enable us to refine the intervention logic model, and to understand key influences on implementation fidelity.

12 Study procedures

12.1 Assessments

Participants will be recruited, assessed at baseline and randomised in the 2021 summer term. The intervention (ZF-SEND) to commence in September of the 2021 Autumn term and continue into the summer term until end the summer term 2022. Post-intervention assessments and qualitative interviews will be completed from May to July 2022. Therefore, all participants (children, teachers and parents/carers) are involved in this study for approx. 12 months.

Children will be seen twice (baseline and post-intervention) for an assessment session with one of the RAs. They will complete the 'Me and My School' questionnaire and two quality of life measures (EQ5D-Y and CHU-9D) with the help of the RA.

Teachers will be asked to complete (for each child participating in the research) three questionnaires: the Nisonger Child Behavior Rating Form (NCBRF), the Strengths and Difficulties Questionnaire (SDQ) and the Emotional Literacy Assessment. They are required to complete these questionnaires during the two assessment periods (baseline and post-intervention) and can choose whether to complete on-line or paper copies. The presence of an RA is not required. Each set of questionnaires (per child) takes approx. 20 minutes to complete and teachers are paid £10 for each set completed.

Parents/carers will be asked during each of the two assessment periods (baseline and postintervention) to complete one set of questionnaires for their child which consists of 5 questionnaires: the parent/carer-rated Strengths and Difficulties Questionnaire (SDQ), the Emotional Literacy Assessment, the two parent/carer-rated Quality of Life (EQ5D–Y and CHU–9D) measures and the Service use parent/carer-rated modified Child and Adolescent Service Use Schedule (CASUS). Parents will be given various options for how to complete these measures: 1/paper copies sent by post; 2/ on-line; 3/ telephone interview with RA; 4/ face-to-face interview with RA. Each set of questionnaires takes approx. 40 minutes to complete. A subsample (N=10 -12) of all three participant groups (children, parents/carers and teachers) will be interviewed as part of the process evaluation (see section 12.2 below) during the follow-up assessment phase (autumn term 2021).

Figure 1 presents the schedule of assessments.

RAs will be trained by the project manager and the CI in interviewing skills (for both quantitative and qualitative components of the assessment) and will have an opportunity to practice their skills before the data collection commences. The measures have been used in earlier studies and have been included because they have been shown to be reliable, valid and acceptable for each of the three participant groups.

Compliance with the intervention (Zippy-SEND manual) and attendance rates of each child participant will be part of the process evaluation (see section 12.2 below).

Figure 1. Schedule of enrolment, interventions and assessments	ns and assessments ¹
--	---------------------------------

Procedures			Visits	
	Screening	Baseline May 2021- July 2021	Treatment= 24 sessions Sept .2021- June 2022	Post Treatment May 2022-July 2022
Informed consent	~			
Demographics (all groups of participants).		~		
Eligibility assessment	✓			
Randomisation		√		
Delivery of intervention			~	✓
Compliance recording			~	✓
Teacher and parent/carer- rated Strengths and Difficulties Questionnaire (SDQ)		~		~
-Teacher–rated Nisonger Child Behavior Rating Form (NCBRF)		~		~

¹ Taken from the HRA CTIMP protocol template (2016).

Teacher and parent/carer-rated Emotional Literacy Assessment	4	~
-Service use (parent/carer-rated modified Child and Adolescent Service Use Schedule; CASUS	¥	~
-Child and parent/carer-rated Quality of Life (EQ5D-Y; CHU-9D)	\checkmark	~
-Child self–report 'Me and My School'	\checkmark	✓
Qualitative interviews with teachers, parents and pupils		✓
Adverse event assessments		

12.2 Process Evaluation

The process evaluation will examine five key aspects of the feasibility of conducting a definitive trial of ZF SEND: 1) intervention recruitment and adherence; 2) intervention implementation; 3) intervention mechanisms, including receipt and acceptability; and 4) the feasibility of implementing ZF SEND within a definitive RCT; 5) description of what constitutes usual practice for emotional literacy in SEND schools.

We will use recent MRC guidance as a framework for the process evaluation to describe implementation processes, refine the intervention logic model through examining intervention mechanisms, and consider the role of school context in shaping intervention implementation and mechanisms. Data from the process evaluation will address key study questions and aid assessment of trial progression criteria.

A mixed methods approach will be utilised. Quantitative methods will be used to assess recruitment rates/patterns (schools, children and parents/carers) and intervention fidelity. Qualitative interviews with children, school staff, parents/carers in intervention arm schools will examine implementation processes, intervention mechanisms, the role of contextual factors, and interrogate patterns in the quantitative data. Interviews will also explore key aspects of the acceptability and feasibility of a future definitive trial of ZF SEND.

Recruitment of schools and families and intervention adherence

Data on recruitment and retention of schools and families to the study (numbers approached, numbers agreeing to take part, and key patterns) will be examined. In intervention schools, staff delivering ZF SEND will be asked to record attendance of pupils at each session to assess adherence. In each intervention school we will interview at least two members of staff (one class teacher involved in the delivery of ZF SEND and a member of the senior management team) to explore their views on trial recruitment methods (acceptability of randomisation, perceived burden on schools) and factors affecting pupil attendance in ZF SEND sessions. We will also ask a member of the senior management team in each control school to participate in a qualitative interview to explore these issues. Factors affecting recruitment and retention will also be explored in interviews parents and carers (see below).

Intervention implementation (addresses study feasibility Q4)

School staff who deliver ZF SEND will be trained in its delivery through successful completion of a one day training course. Qualitative interviews with school staff will examine the perceived quality and value of the training, and we will also conduct interviews with two trainers to explore the extent to which the training was delivered as intended. Fidelity of implementation of ZF SEND sessions in the classroom will be evaluated via self-rating by teachers for all sessions using intervention checklists. This will provide data on: the proportion of sessions delivered; whether each activity within a session is completed/partially completed; any factors which disrupted/aided delivery of activities. In each school we will video record a sample of sessions, which will be coded using the teacher checklist, and an additional tool that covers quality of delivery, any adaptations made to the materials during delivery, class dynamics and contextual issues, with space for free text qualitative observations. Where video recording is not possible (e.g. schools refuse permission) we will use either audio recording or direct observation by a researcher. Rates of agreement to allow video recording, teacher completion of fidelity checklists, and feedback from teachers and research staff will enable us to refine procedures for assessing fidelity within a future definitive trial.

Interviews with 10 -12 school staff will be used to explore: adherence to the ZF SEND manual and key influences on implementation; any additions/adaptations made to the manualised content and the reasons for these; engagement in the intervention by pupils and their parents/carers; the perceived value of ZF SEND, and its fit with existing school policies/priorities; staff views on intervention aims and the mechanisms through which it operates. Data on factors affecting implementation across schools, and variations in fidelity/adaptions will enable us to refine the intervention logic model, and to understand key influences on implementation fidelity.

Intervention mechanisms, including receipt and acceptability

Interviews will be conducted with: a) about 10 - 12 pupils from intervention schools (two per school); and 10 - 12 families from intervention schools (this may include a mix of single and joint interviews if two parents/carers wish to participate together). Interviews with pupils will explore their experience of participating in the intervention, acceptability of intervention content and activities, understanding of key intervention messages, and the extent to which they have used strategies taught. Parents/carers will be asked about whether intervention content taught at school has been used and/or discussed at home with their child, and the extent to which schools have involved them in the intervention (e.g. by sending information home).

Feasibility of implementing ZF SEND within a definitive RCT

Data on school/family recruitment, intervention fidelity and factors shaping implementation processes and intervention mechanisms will be used to help inform assessment of the feasibility of implementing ZF SEND within a definitive trial, including systems and structures needed for recruitment, training and implementation. Qualitative interviews (with school staff in both trial arms, pupils and parents/carers in the trial arm will also explore: a) acceptability of the trial design and randomisation, including preferences regarding the use of a wait list control; b) schools' perception of the burden associated with trial data collection, particularly questionnaire completion by pupils; and c) the acceptability and feasibility of questionnaire measures and fidelity assessment.

Usual Practice

All intervention and control group schools will be asked to complete an interview describing UP in relation to emotional literacy and mental health promotion activities at two time points (prior to baseline data collection and at 12-month follow-up). Qualitative interviews with school staff in intervention and control group schools will explore the provision of usual practice in more detail.

13 Safety reporting

In the unlikely event that any SAEs related to the intervention or research procedures should occur, the CI is responsible for ensuring that all site staff involved in this study are familiar with the content of this section. All SAEs must be reported immediately (and within 24 hours of knowledge of the event) to the study team. SAEs will be assessed at all follow-up time points, and intervention delivery staff will be trained to report these directly to the study team at any point during the study. Rates of SAEs by study arm will be reported to the SSC, and if required, to the REC. Additional information about the potential harm of the intervention will be collected through qualitative interviews with all stakeholders. Interventions such as Zippy's Friends may have side effects for participants or for the classroom as a whole. This will be investigated in the light of any reports.

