5.3 Primary outcomes measure(s)

The feasibility questions to be addressed in the proposed research are the following:

- 1. *Recruitment of schools/children/parents*: What are the most effective recruitment pathways to identify SEND schools? What recruitment rate for parents can be achieved? What are the characteristics of schools and families of children with ID approached, screened and recruited?
- 2. **Recruitment of schools and teachers**: Can sufficient schools and teachers be recruited to run up the ZF SEND programme over one academic year? What factors influence schools' willingness to take part in the research? Can sufficient teachers be recruited and trained?
- 3. **Acceptability of research design**: Are schools and parents willing to be randomised within the context of a RCT? Do they prefer a design with delayed access to ZF SEND in the Usual Practice arm, or will they accept Usual Practice with no access to ZF SEND? How does the offer of delayed access to ZF as part of Usual Practice influence recruitment and retention of schools and pupils?
- 4. **Fidelity of implementation**: Can teachers deliver ZF SEND with a high degree of fidelity to the programme manual? What are the key barriers/ facilitators for successful implementation of ZF SEND and how does this vary across different school contexts?
- 5. *Adherence*: What proportion of children with ID in the intervention arm schools complete the ZF SEND programme?
- 6. *Retention*: What proportion of schools, children and parents/carers are retained in the research study up to the 12-month post-randomisation follow-up?
- 7. **Usual practice**: What does usual practice consist of for the support of well-being on a class-wide curriculum basis for children with ID in special schools? How is usual practice different from the programme content of ZF SEND? Does the offer of delayed access to ZF SEND as part of Usual Practice alter what is offered as part of Usual Practice in the year following randomisation?
- 8. *Estimation of parameters needed to definitive sample size calculation:* What are the estimated standard deviation, intracluster correlation coefficient, average cluster size, and coefficient of variation of cluster size for the SDQ at 12-months post-randomisation?
- 9. *Feasibility of outcome measures*: Do children, teachers and parents complete the outcome measures for the study?

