The comparator intervention will be Usual Practice (UP) - participants will attend their usual classes as well as other services they may be engaged with outside school hours, but without receiving ZF SEND. Because Partnership for Children is the only organisation in the UK offering training in the intervention, there is no possibility of contamination within the control schools during the research. The six schools randomly allocated to the control arm of the study are to receive the same assessment phases as the six intervention schools but will not implement ZF SEND until after 12month follow-up data collection is completed (whether they are in the 'no access' or 'delayed access' sub-group of the UP arm). Records will be kept to monitor group activities and check for potential overlap between UP and ZF SEND contents. UP may include any services (mainstream and specialised) provided to families and their children with ID as a part of an Education Health and Care Plan in England or equivalent in Scotland. We will not include schools/units already delivering a manualised emotional literacy intervention at time of baseline assessments. All other receipt of psychological support or emotional literacy teaching in both arms of the research will be recorded. This will be done using a summary sheet provided for teachers and parents. This will be further explored in qualitative interviews with control arm teachers and parents (see section 8). In addition, services receipt data (see 6.3) collected at baseline and 12 months will be used to fully describe UP.

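### Section 12.2 specifies parent interviews in intervention schools only, although section 11.1 promises control-arm parents, so usual-practice parents are not asked directly whether randomisation and delayed or no access are acceptable

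*Protocol*

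**What the plan says.** Section 12.2 is the operative plan for the interviews. Its general statement places the parent interviews in one arm: "Qualitative interviews with children, school staff, parents/carers in intervention arm schools will examine implementation processes". Under the heading on intervention mechanisms it sets the family sample as "10 - 12 families from intervention schools". A separate paragraph, on feasibility within a definitive trial, names the respondents on design: "Qualitative interviews (with school staff in both trial arms, pupils and parents/carers in the trial arm will also explore", followed by the topic "acceptability of the trial design and randomisation, including preferences regarding the use of a wait list control". The usual-practice (UP) paragraph names staff only: "Qualitative interviews with school staff in intervention and control group schools will explore the provision of usual practice in more detail".

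Section 11.1, in its comparator text, describes the recording of other support and emotional literacy teaching, then adds: "This will be further explored in qualitative interviews with control arm teachers and parents (see section 8". Section 8 is participant selection and has no interview plan.

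Sections 5.2(iii) and 6 say that some parents will be interviewed to describe UP. They give no arm, number or procedure. Section 12.1 gives an interview subsample of 10-12 for each participant group, with no arm stated.

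Feasibility question 3 in section 5.3 is addressed to schools and parents. It asks about willingness to be randomised and about preference: "Do they prefer a design with delayed access to ZF SEND in the Usual Practice arm". It then raises the alternative of a comparator that never offers the programme: "or will they accept Usual Practice with no access to ZF SEND".

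**The concern.** The protocol commits to control-arm parent interviews in one place and makes no provision for them where the interviews are specified. A team working from 12.2 would recruit no UP parents, and one working from 11.1 would be sent to a section with nothing to follow.

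The gap falls on a primary feasibility question. Whether a no-access or delayed-access comparator is acceptable to parents bears directly on the choice of comparator for the definitive trial. Parents in UP schools are the ones living with that comparator. Parents in intervention schools can speak from experience about being asked to join a randomised study, but only hypothetically about going without the programme.

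**Working it through.** There is no statistical figure to reproduce. The check sets the sections side by side and counts what is specified.

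| Place in the protocol | Which parents | Number | Topic |
|---|---|---|---|
| 5.2(iii) and 6 | arm not stated | not stated | what UP consists of |
| 11.1, comparator | control arm | not stated | other support and emotional literacy teaching |
| 12.1 | arm not stated | 10-12 | process evaluation |
| 12.2, general statement | intervention arm | not stated | implementation, mechanisms, context |
| 12.2, mechanisms | intervention schools | 10-12 | use at home, involvement by the school |
| 12.2, definitive trial | 'the trial arm' | not stated | randomisation, wait-list preference, burden, measures |
| 12.2, usual practice | none (staff only) | none | what UP consists of |

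**Step 1: the count.** The only family sample with both a number and a source is the 10-12 from the six intervention schools. It equals the 10-12 for parents in 12.1. The specified number left for the six UP schools is therefore 10-12 minus 10-12, which is 0.

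**Step 2: how firm that zero is.** The 10-12 in 12.1 should not be read as a hard ceiling. For staff, 12.2 asks for at least two in each of six intervention schools (2 × 6 = 12) and one senior manager in each of six control schools (1 × 6 = 6). That makes 18, already above the 10-12 given for teachers, though 12.1 may mean class teachers only. So the zero is what is specified for UP families. It does not show that such interviews are ruled out.

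**Step 3: 'the trial arm'.** The phrase is loose and its bracket is never closed. Three things point to the intervention arm: the contrast with staff in both arms within the same sentence, the intervention-school sample given just before it, and the general statement at the start of 12.2. Where 12.2 wants control-arm input it says so, as with the senior manager in each control school. It says nothing equivalent for parents.

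**Step 4: topic.** The promises in 5.2(iii), 6 and 11.1 concern what UP consists of. None of them covers whether randomisation or lack of access is acceptable. Honouring 11.1 alone would therefore still leave this part of question 3 unasked of UP parents.

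**The case against.** The strongest reply has three parts.

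First, the restriction to intervention schools sits under the mechanisms heading. Only families whose child received the programme can say whether its content was used at home. That is right, and the restriction is sound for that component. It does not justify limiting the design-acceptability questions, which come in another paragraph.

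Second, the wider intent is on record. Sections 5.2(iii), 6 and 11.1 foresee broader parent interviews, section 9.1 describes the interview subgroup as assenting parents with no arm limit, and section 13 mentions interviews with all stakeholders about harm. This stands. The fault is that the sections are unreconciled, and the protocol shows no decision to leave UP parents out.

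Third, question 3 has other sources. A reader might infer that it would be answered only by parents whose child received the programme. The protocol does not support that:

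- Parents are approached and pupils enrolled before schools are randomised (9.5.1), so parent recruitment reflects willingness in both future arms.
- The nested study of two information sheets (section 6) examines how a delayed-access offer affects recruitment and retention.
- Retention is a feasibility question in its own right (5.3), and data are reported by arm (15.1).
- Senior managers in control schools are interviewed about randomisation (12.2).

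A reader might also infer that dropout among control families would be missed. Section 10.2 has the number lost and the reasons recorded, through liaison with schools and parents and with no limit by arm. Nor do the documents show that intervention parents' answers would lean towards acceptability; the direction of any bias is unknown.

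These sources show what parents did and, for those who left, a recorded reason. They do not give the views of UP parents who stayed, or their preference between delayed and no access.

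**Conclusion.** The point holds as an inconsistency with a limited but real consequence. Section 11.1 promises control-arm parent interviews through a pointer that leads nowhere, and 12.2 specifies 0 of its 10-12 family interviews in the six UP schools. Followed as written, 12.2 yields no interview data from UP parents on randomisation or on delayed versus no access, although a primary feasibility question asks this of parents. The other data inform that question indirectly.

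The conclusion rests on two readings: that 12.2 governs the conduct of the interviews, and that 'the trial arm' means the intervention arm. If the second is wrong, the wording still has to be corrected, because it names no arm clearly and no sample of UP families stands behind it.

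**What to change.** 1. Reconcile sections 5.2(iii), 6, 11.1, 12.1 and 12.2 on which parents are interviewed, how many, and on what. Correct the section 8 pointer in 11.1 so that it leads to 12.2.
2. Amend 12.2 so that the parent interviews include control-arm families and state their number. Draw them from both information-sheet versions as far as both occur among the six UP schools. The minimisation balances on school size and study site, so it does not ensure an even split by sheet version.
3. In the design-acceptability sentence, replace 'parents/carers in the trial arm' with parents/carers in both arms. Aligning 12.2 with 11.1 is not enough by itself, because 11.1 covers only the content of UP.
4. Keep the mechanism and home-use questions for intervention families.

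The cost is small. If the total stays at 10-12, no interviews are added, but somewhat fewer intervention families remain for the mechanism questions. A few additional UP interviews would avoid that loss, at the price of the extra fieldwork. Either choice is defensible, provided that it is stated.
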